3.3. Discontinuation from Study Treatment

Patients will be discontinued from study treatment for any of the following reasons:

- Disease progression (patients who are receiving clinical benefit in the opinion of the treating Investigator may be allowed to stay on study after consultation with the Medical Monitor).
- Intolerable toxicity or abnormal laboratory values thought to be related to drug toxicity.
- Conditions requiring therapeutic intervention not permitted by the protocol.
- Intercurrent illness that may interfere with the patient's ongoing participation in the study (this will be at the Investigator's discretion).
- Inability of the patient to comply with study requirements.
- Patient lost to follow-up.
- Patient requests to discontinue treatment.
- Patient withdraws consent from study participation altogether.
- Pregnancy.
- Study termination.

After discontinuation from protocol treatment, patients must be followed for AEs for 30 days after their last dose of study drug. All new AEs occurring during this period must be reported and followed until resolution unless, in the opinion of the Investigator, these values are not likely to improve because of the underlying disease. In this case, the Investigator must record his or her reasoning for this decision in the patient's medical records and indicate on the AE pages of the electronic case report form (eCRF) that the outcome is not resolved.

All patients who have Grade 3 or 4 laboratory abnormalities (per NCI [CTCAE Version 5.0](#)) at the time of discontinuation must be followed until the laboratory values have returned to Grade 1 or 2 unless it is, in the opinion of the Investigator, not likely that these values are to improve. In this case, the Investigator must record his or her reasoning for making this decision in the patient's medical records and indicate on the AE pages on the eCRF that the outcome is not resolved.

4. STUDY DESIGN

This is a Phase 1/2, open-label, 2-part study of an inhibitor of allosteric *ErbB* mutations, BDTX-189, given as a single oral agent. The study schema is shown in [Figure 10](#).

4.1. Part A (Phase 1 - Dose Escalation and Safety Expansion)

Part A (Phase 1) is designed to determine the RP2D and schedule of BDTX-189 as a single agent. The RP2D will be based on the safety, tolerability, PK, food effect, and preliminary antitumor activity of BDTX-189 and will not exceed the MTD (see Section [4.3.3](#)).

BDTX-189 will be given PO QD on a 21-day schedule in escalating doses. Accelerated titration has been performed with single-patient cohorts at 25, 50, 100, and 200 mg QD followed by multiple-patient cohorts of 400, 800, and 1200 mg QD in fasting state. After the SRC determined 1200 mg QD fasting exceeded the MTD, 800 mg, and 1000 mg QD administered with a meal (i.e., NF) were evaluated.

In addition, a parallel, dose-escalation of BDTX-189 being administered BID is being evaluated. The SRC determined to initiate the BID evaluation at 800 mg BID, which was subsequently de-escalated to 600 mg BID. A dose of 400 mg BID will also be evaluated.

The Safety Expansion cohort(s) at the MTD or lower dose for the QD and/or BID schedule of up to approximately 48 additional patients (including a minimum of 12 patients who may receive the smaller and reformulated 200 mg tablet strength [see Section [6.1.1](#)]) will be enrolled to further evaluate the safety, PK, and preliminary efficacy of BDTX-189 while administrative steps are taken to open enrollment in Part B of the study. Patients in Part A who initiated treatment with the larger 200 mg tablet may be switched to the smaller and reformulated 200 mg tablet at the beginning of their subsequent cycles as instructed by the Sponsor.

After the SRC deemed the 400 mg QD dose regimen was tolerable, a fed (high- or low-fat meal)/fasted randomized crossover, single-dose, lead-in phase was initiated (in up to 16 PK-evaluable patients) to assess the effect of food on the PK of 400 mg BDTX-189 (see [Table 1](#) and Section [5.3.1](#)). Enrollment of the Food-Effect cohort and next dose cohort (800 mg QD Dose Expansion cohort) was done in parallel with priority for enrollment given to the 800 mg QD cohort.

Patients in Part A who terminate participation in the study for any reason other than DLTs before completing Cycle 1 and patients who do not receive at least 75% of the planned doses of BDTX-189 in Cycle 1 for any reason other than DLT-related interruptions will be considered non-evaluable (NE) for DLTs, and additional patients may be enrolled to ensure an adequate number of DLT-evaluable patients. Additional patients may also be enrolled if there are patients who are deemed NE for food effect PK assessment.

Patients who experience a DLT but who, in the opinion of the Investigator, are deriving clinical benefit will be permitted to continue treatment with BDTX-189 at a lower dose that has been demonstrated to be well tolerated upon resolution of the DLT. In total approximately 128 patients will be enrolled in Part A.

4.2. Part B (Phase 2)

Part B is a Phase 2, open-label, multicenter basket study to determine the antitumor activity and safety of BDTX-189 in adult patients who have a solid tumor harboring an oncogenic allosteric [REDACTED] mutation or an [REDACTED] or [REDACTED] mutation from one of the 7 MTCs (Appendix I). Mutation testing, performed by a validated and CLIA-certified NGS assay routinely used by each institution, must be performed using tissue and/or plasma. Baseline tumor tissue for retrospective concordance testing by a companion diagnostic test is mandatory.

Each patient must have a tumor harboring 1 of the eligible [REDACTED] mutations or 1 of the eligible [REDACTED] or [REDACTED] mutations (see Appendix I). Eligible patients will be assigned to 1 of the following 5 cohorts:

Cohort 1: NSCLC with an [REDACTED] mutation from MTC-A

Cohort 2: NSCLC with an [REDACTED] mutation from MTC-B or point mutation from MTC-C

Cohort 3: Breast cancer with an [REDACTED] mutation from MTC-B, MTC-C, MTC-D, MTC-E, or MTC-F

Cohort 4: NSCLC, biliary tract cancer, or cervical cancer with an [REDACTED] mutation from MTC-D

Cohort 5: Any solid tumor type with any allosteric *ErbB* mutation from any of the 7 MTCs (MTC-A to MTC-G), excluding patients who are otherwise eligible for Cohorts 1-4

[figure not shown]
BDTX-189 will be evaluated at the RP2D determined in Part A (800 mg, daily total dose) in each of the 5 separate cohorts described above, which reflect an interest in testing the hypothesis that the drug is active against a broad range of *ErbB* allosteric mutations and cancer types, supported by the pre-clinical data (see Section 1.1.5) and the proof of principle demonstrated by other investigational drugs in the same class in patients with NSCLC harboring exon 20 insertion mutations, and breast cancer and other solid cancers harboring [REDACTED] mutations (see Section 1.1.4 and 1.1.5). In total approximately 491 patients will be enrolled in Part B.

Separate null hypotheses and targeted ORR values are established for each cohort (see Section 9.3.2) to permit evaluation of potentially different antitumor activity of BDTX-189 in response to different cancer and mutation pairs. The target response rates reflect several key observations: (1) patients with NSCLC harboring [REDACTED] or [REDACTED] mutations remain a cancer population with currently no approved therapies and therefore has an unmet medical need. Investigational therapies targeting NSCLC patients with [REDACTED] or [REDACTED] mutations have achieved response rates of about 20-40% in Phase 2 trials (see Section 1.1.4 and 1.1.5); (2) Patients with advanced breast cancer harboring some common [REDACTED] mutations have achieved a response rate of 24% with single-agent neratinib, a pan-[REDACTED] TKI (Hyman et al. 2017); (3) NSCLC, biliary or cervical cancers with an [REDACTED] mutation from MTC-D (including, but not limited to S310F and S310Y) demonstrated anecdotal responses on single-agent neratinib while other solid cancers did not (Hyman et al. 2017).

To minimize exposing patients that may be unresponsive to BDTX-189 therapy in Part B, each cohort will have either 1 or 2 futility analyses to evaluate the treatment effect before the cohort proceeds to full enrollment. The detailed futility analysis plan including sample size and

stopping rules for each cohort is described in [Section 9.3.2](#). The study schema is presented in [Figure 10](#).

Figure 10 Study Schema

1. The Dose Escalation in Part A will start with a QD regimen.

2. The dose evaluated for the BID regimen will be initiated at 800 mg.

* The actual number of cohorts per step will be data-driven.

Note: Up to 48 patients will be included in the Safety Expansion cohort(s).

[Yuan et al. 2016](#).

4.3. Treatment Plan

BDTX-189

BDTX-189 will be provided as tablets for oral administration in dose strengths of 100 and 200 mg. Additionally, a smaller and reformulated 200 mg tablet will be administered to some patients at select sites enrolling in the Safety Expansion of Part A and all patients enrolling onto Part B.

Prior to exceeding the MTD for the QD schedule, patients received BDTX-189 in a fasted state. As of January 2021, based on the recommendation of the SRC (details provided in Section 1.1.7), all patients will receive BDTX-189 with approximately 240 mL water within 30 minutes of completing a meal (Section 6.1.2). The time of day for BDTX-189 administration should be consistent. For patients receiving BDTX-189 BID, the 2 doses should be separated by at least 10 hours.

Patients enrolling into the Food Effect cohort will be dosed in the fed/faasted state as per [Table 1](#) and Section 5.3. On scheduled PK collection days (Cycle 1 Day 1 and Cycle 1 Day 15 for Part A, and Days -4 and -1 for the Food Effect Cohort), patients will be instructed to wait until they arrive at the study center to take their study drug when told.

In Part B, patients will be administered BDTX-189 at the RP2D identified during Part A (800 mg QD, non-fasting).

If the patient misses a dose of study drug, the patient should take the dose as soon as possible but not less than 12 hours before the next dose is due for QD dosing. If the next dose is due in less than 12 hours, the patient should skip the missed dose and take the next dose as scheduled. If the patient in a BID cohort misses a dose of study drug, the patient should take the dose as soon as possible but not less than 6 hours before the next dose is due for BID dosing. If the next dose is due in less than 6 hours, the patient should skip the missed dose and take the next dose as scheduled.

If vomiting occurs more than 30 minutes after taking the study treatment, the patient should be instructed not to retake that dose. Patients should take the next scheduled dose of BDTX-189. If vomiting persists, the patient should contact the Investigator.

BDTX-189 dosing compliance will be reviewed with the patient at the beginning of each new treatment cycle when the study drug is dispensed. A cycle will be 21 days. All patients will be required to complete a paper dosing diary, which must be returned to the clinic for review at each visit. The patient should be instructed to record each date and time the dose(s) were taken in the dosing diary. If a dose is missed, the reason must be noted in the diary.

Patients should be advised to return any unused BDTX-189 in the original bottles, in addition to returning any empty bottles. Any remaining empty study drug bottles and dosing diaries will be given to the study staff at the End-of-Treatment (EOT) visit.

No routine anti-diarrheal agents will be given preemptively. However anti-diarrheal agents should be administered in the event of diarrhea to manage the symptoms (see [Table 8](#)).

Prophylactic anti-emetics are allowed for nausea and/or vomiting. Oral ondansetron may be used after consultation with the Sponsor.

Table 5 Dose Levels Projected for Evaluation (Part A)

QD Cohort - Dose Level	Total Daily Dose (QD)	BID Cohort – Dose Level	Total Daily Dose (BID) ^a
1 (starting dose)	25 mg		
2	50 mg		
3	100 mg		
4	200 mg		
5	400 mg	1 (earliest starting dose)	400 mg
6	800 mg	2	800 mg
7	1200 mg	3	1600 mg
8	1600 mg	4	2000 mg

Abbreviations: BID = twice daily; QD = once daily

^a Alternative dosing schedule (BID) evaluation may or may not be initiated. If the BID schedule is evaluated, the first dose level may not be initiated until dose level 4 of the QD schedule is declared tolerable by the Safety Review Committee. The QD and BID schedule, if opened, will be assessed and escalated independently.

4.3.1. Dose-Escalation Procedure

The actual number of dose cohorts to be explored in this study will depend on determination of the MTD based on DLTs reported during the DLT evaluation period (Day 1 to Day 21 in Cycle 1 [Part A]).

In order that sufficient PK data are collected at doses below the MTD, additional patients may be enrolled at lower doses.

The Bayesian Optimal Interval Design

A Bayesian optimal interval (BOIN) design (Liu and Yuan 2015; Yuan et al. 2016) will be used to find the MTD (Appendix G). For this study, the target toxicity rate for the MTD will be $\phi = 0.3$ and the maximum sample size will be 36 evaluable patients for the QD schedule, excluding patients in the accelerated titration step. The BOIN study design is described in the following steps:

1. Accelerated titration will be performed as follows: the first patient will be treated at QD dose level 1. If no \geq Grade 2 AE related to BDTX-189 is observed during Cycle 1, the dose will be escalated to the next higher level for the next patient enrolled. One additional patient may be enrolled to ensure at least 1 patient is DLT-evaluable. This one-patient-per-dose escalation process will be continued until any \geq Grade 2 AE related to BDTX-189 is observed, and then an additional 2 patients will be treated at the dose at which the AE is observed. If no \geq Grade 2 drug-related AE is observed by dose level 4 (200 mg QD), then enrollment into dose level 5 will proceed. Thereafter, patients will be treated in cohorts as described in steps 2 and 3.
2. To assign a dose to the next cohort of patients, dose escalation/de-escalation will be conducted according to the rules in Table 6, which minimize the probability of incorrect dose assignment.

3. Step 2 will be repeated until the maximum sample size of 36 DLT-evaluable patients, without including the patients treated in the accelerated titration step, is reached or the trial will be stopped if the number of patients treated at the current dose reaches 15.

Table 6 Dose Escalation/De-escalation Rules for Bayesian Optimal Interval Design Once Daily Dosing

Actions	The number of patients treated at the current dose														
	1	2	3	4	5	6	7	8	9	10	11	12	13	14	15
Escalate if # of DLT \leq	0	0	0	0	1	1	1	1	2	2	2	2	3	3	3
De-escalate if # of DLT \geq	1	1	2	2	2	3	3	3	4	4	4	5	5	6	6
Eliminate if # of DLT \geq	NA	NA	3	3	4	4	5	5	5	6	6	7	7	8	8

Abbreviations: DLT = dose-limiting toxicity; NA = not applicable.

Please note the following:

- “Eliminate” means eliminate the current and higher doses from the trial to prevent treating any future patients at these doses because they are overly toxic.
- When a dose is eliminated, the dose is automatically de-escalated to the next lower level. When the lowest dose is eliminated, the trial is stopped for safety. In this case, no dose should be selected as the MTD.
- If the decision is to escalate the dose and the next higher dose has been eliminated due to high toxicity, new patients are treated at the current dose. Alternatively, a new intermediate dose between the current dose and the eliminated dose may be added (increment between 25% and 50% of the current dose) or if the next higher dose has not been eliminated but the current dose level is associated with non-DLTs; then new patients are treated at the added intermediate dose (increment between 50% and 75%).
- If none of the actions (i.e., escalation, de-escalation, or elimination) is triggered, new patients are treated at the current dose.
- If the current dose is the lowest dose and the rule indicates dose de-escalation, new patients are treated at the lowest dose unless the number of DLTs reaches the elimination boundary, at which point the trial is terminated for safety.
- If the current dose is the highest dose and the rule indicates Dose Escalation, new patients are treated at the highest dose. Alternatively, a new higher dose (increment not greater than 25% of current dose) may be added; then new patients are treated at the added dose.

After each cohort of a minimum of 1 patient in the accelerated titration step and 3 patients in steps 2 and 3 have been enrolled and completed Cycle 1, the SRC will review the safety data and determine whether to proceed with further dose escalation. Safety and tolerability data obtained in patients past Cycle 1 may also be considered, as appropriate. More than 3 patients per cohort may be enrolled at the current dose level, as shown in [Table 6](#). If 1 DLT is observed at the current dose, between 5 and 8 patients must complete Cycle 1 and be evaluable for DLT assessments before a decision to proceed with further dose escalation is made.

The operating characteristics of this BOIN design based on simulations of various scenarios are shown in [Appendix G](#).

After Part A is completed, the MTD will be selected based on isotonic regression. Specifically, the dose for which the isotonic estimate of the toxicity rate is closest to the target toxicity rate is

the MTD that will be selected. If there are ties, the higher dose level will be selected when the isotonic estimate is lower than the target toxicity rate, and the lower dose level will be selected when the isotonic estimate is greater than or equal to the target toxicity rate.

Once the MTD has been determined (MTD may be QD or BID), up to 48 additional patients (including 12-24 patients for PK evaluation of a smaller and reformulated 200 mg tablet) may be enrolled at the MTD or a lower dose if deemed relevant, to obtain additional experience with safety and efficacy. The elimination boundaries in [Appendix H](#) will be used for toxicity monitoring.

BID Dose Schedule Evaluation

In the event that PK, tolerability, or PDx analysis suggests that a more frequent daily dosing schedule should be explored, a BID dose schedule will be evaluated and a separate BOPN design will be used to find the MTD using that dosing schedule. The design parameters will depend on the specific PK/PDx and tolerability results and the cumulative observations from the QD Dose Escalation study. The BID schedule will not be initiated until dose level 4 (200 mg QD) of the QD schedule has been deemed tolerated or until the MTD has been determined for the QD schedule (see [Table 5](#)). The BID schedule may also be initiated at higher dose levels as determined by the SRC based on emerging safety and PK data. Should a Dose Escalation for the QD schedule be eliminated before reaching the highest dose, then BID Dose Escalation may be pursued independently.

The target toxicity rate for the MTD will remain $\phi = 0.3$, and patients will be enrolled and treated in cohorts with no accelerated titration phase. The Dose Escalation/de-escalation rules will be the same as shown in [Table 6](#) and [Appendix H](#).

If 4 dose levels are evaluated and the maximum sample size is 24, the study will continue until 24 patients have been treated or if the number of patients treated at the current dose reaches 15.

4.3.2. Dose-limiting Toxicity

Toxicity will be assessed using the NCI [CTCAE Version 5.0](#) unless otherwise specified.

A toxicity will be considered dose-limiting (unless clearly attributable to an extraneous cause, such as underlying disease) if it occurs during the first cycle (21 days) of treatment with BDTX-189. Dose-limiting toxicities (DLTs) will be defined as follows:

- Any death not clearly due to the underlying disease or extraneous causes.
- Hematologic toxicity
 - Grade 4 neutropenia or thrombocytopenia for >7 days or febrile neutropenia.
 - Grade 3 thrombocytopenia associated with bleeding or requiring a platelet transfusion.
 - Grade ≥ 4 anemia.
- Non-hematologic toxicity of \geq Grade 3 (at any time during treatment) that, in the judgment of the Investigator, is dose-limiting except for:
 - Grade 3 fatigue lasting <1 week.
 - Grade 3 nausea, vomiting, or diarrhea lasting <5 days without adequate supportive care.

- Grade 3 nausea, vomiting, or diarrhea lasting <24 hours with adequate supportive care.
- The following non-hematologic laboratory abnormalities:
 - Baseline Grade ≤ 1 ALT or AST: any drug -related Grade ≥ 3 abnormality of ALT and/or AST or increase in ALT or AST $>3 \times$ ULN with a concurrent increase in total bilirubin $>2 \times$ ULN (per Hy's Law).
 - Baseline Grade ≥ 2 ALT or AST due to liver metastases: any drug-related ALT and/or AST $>2 \times$ baseline or $\geq 10 \times$ ULN.
- Dose reduction during Cycle 1 due to an AE related to BDTX-189.
- Delay of starting Cycle 2 for >2 weeks if due to an AE related to BDTX-189.
- Interruption of BDTX-189 dosing for more than 7 days during Cycle 1, if due to a drug-related AE.

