
	the associated 2-sided 95% CIs will be provided. Additional exploratory and confirmatory analysis may be performed.
--	---

Table 1 BDTX-189-01 Schedule of Assessments Part A-Dose Escalation Including Food-Effect Cohorts

Flow Chart (Part A Dose Escalation including food-effect cohorts) Study period	Screening	Lead-in Phase Food Effect-Dose level 5 (400 mg QD) or higher		Part A Dose Escalation BDTX-189 Treatment Period										
Study Procedures ^a				Cycle 1 (±1 day for Days 8, 15)			Cycle 2 (±2 days)			Cycle 3, 4, 5 and every other cycle thereafter (±2 days)		End of Treatment ^c	30-Day Safety Follow-up Visit ^d	Un-scheduled Visits ^e
Study Day	≤28 days prior to C1D1	-4	-1	1 ^b	8	15	1	8	15	1	Within 3 days of decision to discontinue study drug	30 days after last dose (±3)		
Informed consent	X ^f													
Inclusion / exclusion criteria	X													
Medical and disease history	X													
Demographics	X													
Complete physical exam ^g	X			X			X			X	X			
Directed physical exam ^g					X	X		X	X			X	X	
Weight	X			X ^h						X	X	X		
ECOG Performance Status	X			X ^h			X			X	X	X	X	
Vital signs ⁱ	X			X	X	X	X	X	X	X	X	X	X	
12-lead ECG ^j	X			X ^k		X ^k	X			X	X	X	X	
ECHO/MUGA ^l	X									X ^l	X		X	
Hematology (CBC with 5-part differential and platelets) ^m	X			X ^{h,m}	X	X	X			X	X	X	X	
Clinical chemistry ^{m,n}	X			X ^h	X	X	X	X	X	X	X	X	X	

Study Drug: BDTX-189

Sponsor/Development Innovations Study Numbers: BDTX-189-01/REFMAL 648

Protocol Amendment 3 (Version 4.0): 08 June 2021

Flow Chart (Part A Dose Escalation including food-effect cohorts) Study period	Screening	Lead-in Phase Food Effect-Dose level 5 (400 mg QD) or higher		Part A Dose Escalation BDTX-189 Treatment Period										
Study Procedures ^a				Cycle 1 (±1 day for Days 8, 15)			Cycle 2 (±2 days)			Cycle 3, 4, 5 and every other cycle thereafter (±2 days)		End of Treatment ^c	30-Day Safety Follow-up Visit ^d	Un-scheduled Visits ^e
Study Day	≤28 days prior to C1D1	-4	-1	1 ^b	8	15	1	8	15	1	Within 3 days of decision to discontinue study drug	30 days after last dose (±3)		
Coagulation (PT, aPTT, INR) ^{h,m}	X			X ^h			X			X	X			
Urinalysis ^{m,o}	X			X ^h			X			X	X	X	X	
Pregnancy test ^p	X						X			X	X		X	
PK sample collection ^q				X		X	X			X				
ctDNA sample collection ^r				X			X			X ^r	X ^r			
Food administration for food effect ^s		X	X											
PK sample collection for food effect ^t		X	X			X	X			X				
Archival tissue sample ^u	X													

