Grade 3-4	Permanently discontinue BDTX-189. Closely monitor LVEF until resolution or for up to 16 weeks.
All other BDTX-189 treatment-related adverse events	
Grade 1 or 2 (except fatigue, alopecia, and laboratory abnormalities not requiring medical intervention)	Maintain dose level if the event is Grade 1 or non-persistent Grade 2. If the event is persistent Grade 2 not responding to a specific therapy, consider $\downarrow 1$ dose level.
Grade 3	Omit dose until resolved to \leq Grade 1 or baseline level, then $\downarrow 1$ dose level
Grade 4	Discontinue patient from study treatment

Abbreviations: ALT = alanine aminotransferase; AST = aspartate aminotransferase; ECG = electrocardiogram; LLN = lower limit of normal; LVEF = left ventricular ejection fraction; NCI CTCAE = National Cancer Institute Common Terminology Criteria for Adverse Events; QTcF = QT interval corrected according to Fridericia's formula; ULN = upper limit of normal. Note: After the MTD was exceeded for the QD and BID schedules in fasted state, subsequent cohorts were evaluated non-fasted (fed). For Dose reduction levels refer to [Table 7](#).

Intrapatient dose-escalation during Part A may be considered in the absence of \geq Grade 2 toxicities related to BDTX-189 in the following circumstance: After a new higher dose level has been determined to be tolerated ($\leq 30\%$ DLTs), any patients remaining on study and being treated with a lower dose of BDTX-189 may, at the discretion of the Investigator and with agreement of the Sponsor, be offered treatment at the new higher tolerated dose once that dose level evaluation has been cleared. During the Safety Expansion and Part B, re-escalation of BDTX-189 following dose reduction due to toxicities may be considered following discussion and approval of Sponsor's Medical Monitor.

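### Section 4.3.2 counts Grade 3 thrombocytopenia with bleeding or transfusion as a DLT at any duration but Grade 4 only beyond 7 days, so a shorter Grade 4 event with bleeding or transfusion meets no platelet bullet

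*Combined protocol and SAP*

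**What the plan says.** Section 4.3.2 (Dose-limiting Toxicity) has two bullets that cover platelets. The first reads "Grade 4 neutropenia or thrombocytopenia for" more than 7 days (febrile neutropenia is in the same bullet). The second reads "Grade 3 thrombocytopenia associated with bleeding or requiring a platelet transfusion" and has no duration condition. The general bullet for Grade 3 or higher events is limited to non-hematologic toxicity, and to toxicity "that, in the judgment of the Investigator, is dose-limiting except for" a short list of exceptions.

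Three further bullets depend on dosing: a Cycle 1 dose reduction for a related event, "Interruption of BDTX-189 dosing for more than 7 days during Cycle 1, if due to a drug-related AE", and "Delay of starting Cycle 2 for >2 weeks if due to an AE related to BDTX-189".

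Table 8 (Section 4.3.5) has no platelet row. A related Grade 4 event without its own row has the action "Discontinue patient from study treatment". Discontinuation is not itself on the DLT list.

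Section 9.2 makes the Cycle 1 DLT rate the primary Part A estimand. Section 4.3.1 applies Table 6 to both the QD and BID schedules, and monitors the Safety Expansion (up to 48 patients) against the elimination boundaries in Appendix H. Section 1.1.7 says that 400 mg BID is enrolling.

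**The concern.** A DLT rule should not score a worse event more leniently than a milder one of the same kind. Here, a patient who bleeds or is transfused at Grade 3 for a few days is a DLT. The same patient with a Grade 4 count over the same days is not, on the platelet bullets alone. The authors probably meant Grade 3 or higher, but the text does not say so. The anemia bullet and the non-hematologic bullet beside it do carry a ≥ sign, so a site cannot assume that one was implied.

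At stake is consistent scoring of a rare but serious event. Two sites could score the same patient differently, and in a small BID cohort one DLT can change the Table 6 action.

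**Working it through.** The plan states no figure for this point, so the check is to apply the bullets case by case and then read the consequence from Table 6.

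**Platelet bullets as written (Section 4.3.2)**

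| Grade | Bleeding or transfusion | 3 days | 7 days | 8 days |
|---|---|---|---|---|
| 3 | no | not met | not met | not met |
| 3 | yes | DLT | DLT | DLT |
| 4 | no | not met | not met | DLT |
| 4 | yes | **not met** | **not met** | DLT |

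The bottom row is the inversion. With Grade ≥3 in the second bullet, its two unmet cells become DLTs and no other cell changes.

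**Other routes for the bottom-row patient**

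- *Bleed as a non-hematologic event.* This needs a bleed of Grade 3 or higher and the Investigator's judgment that it is dose-limiting. It does not reach a lesser bleed, or a transfusion without bleeding.
- *Discontinuation read as an interruption of more than 7 days.* If dosing stops from Day d, the Cycle 1 days without drug are 22 − d. Day 14 gives 22 − 14 = 8, which qualifies. Day 15 gives 22 − 15 = 7, which does not. The route also requires a permanent stop to be read as an interruption.
- *Discontinuation read as a Cycle 2 delay of more than 2 weeks.* This works for a stop on any day of Cycle 1, but only if a Cycle 2 that never starts is read as one that is delayed.
- *Recovery through Grade 3.* If the count rises to Grade 3 while the patient is still bleeding or needing transfusion, the second bullet is met. This depends on how the event resolves.
- *Dose reduction or death.* Each is a DLT, but Table 8 calls for discontinuation of a related Grade 4 event, not reduction.

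None of these follows automatically from the event itself.

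**What one added DLT does in Table 6**

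| Evaluable n | Escalate if DLTs ≤ | De-escalate if DLTs ≥ | Reading |
|---|---|---|---|
| 3 | 0 | 2 | 1/3 stay; 2/3 de-escalate |
| 6 | 1 | 3 | 2/6 stay; 3/6 de-escalate |
| 9 | 2 | 4 | 1/9 still reads escalate |

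The number evaluable at 400 mg BID is not given, so n = 3 and n = 6 are illustrations. There, one event can move the action from stay to de-escalate. At 800 mg QD no DLT was reported (Section 1.1.7), and a single DLT never reads de-escalate at any n of 3 or more. Nine patients were treated at 800 mg QD non-fasting. If all nine were evaluable (the number is not stated), de-escalation would need 4 of 9.

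**The case against.** The strongest reply is that the gap is narrow and the event unlikely. Table 8 takes a patient with related Grade 4 thrombocytopenia off treatment, and it would be odd to call that tolerable when Cycle 2 never starts. A serious bleed can be scored in its own right. The Safety Review Committee also sees laboratory abnormalities that are not DLTs (Section 10.3.1). Section 1.2.1 reports no related Grade 4 or 5 event. The DLTs listed in Section 1.1.7 are gastrointestinal, hepatic, creatinine and dehydration events. Section 1.2 notes platelet increases, not falls, in dogs at higher doses.

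All of this stands as a limit on size. It does not repair the rule, because each fallback asks the reader to interpret a bullet written for something else, and the direct correction is one symbol.

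Two stronger points might be inferred, and the documents do not support either.

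- *That the more-than-7-day condition cannot be shown on weekly scheduled counts.* Table 1 allows unscheduled hematology as clinically indicated. Sections 8.1.6 and 8.2.2 require start and end dates, with separate entries when severity changes.
- *That the ALT/AST limits are inverted in the same way.* If Grade 3 is read against baseline, as Table 8 prints it for abnormal baselines, the limit is 5 × 3.0 = 15 × ULN at a baseline of 3.0 × ULN and about 2 × 3.0 = 6 × ULN just above. Read against ULN, it goes from 5 to about 6 and there is no inversion. Section 4.3.2 does not say which reading applies, and exclusion criterion 1c confines such baselines to patients with liver metastases. This is a request for clarification, not a demonstrated error.

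**Conclusion.** The platelet wording is wrong as written and should be corrected. Grade 4 thrombocytopenia of 7 days or less with bleeding or transfusion meets no platelet bullet, while the milder Grade 3 event counts at any duration.

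A reader might infer that such an event could never be a DLT, that one has been missed, or that the 800 mg QD dose is in doubt. None of these follows. Other routes exist, the documents show no misclassified patient, and one added event would not change the 800 mg QD decision. The practical effect so far is probably nil. It could matter for a future patient in a small 400 mg BID cohort or in the Safety Expansion. The conclusion takes Grade 3 literally, as the neighbouring bullets' use of ≥ suggests it should be taken.

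**What to change.** In the bleeding/transfusion bullet of Section 4.3.2, replace Grade 3 with Grade ≥3 and leave the rest unchanged. Apply it to the ongoing 400 mg BID cohort and to Safety Expansion monitoring. Check the Cycle 1 platelet data already held (45 DLT-evaluable patients at the 02 April 2021 cut, plus later enrolments) against the corrected bullet.

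The cost is a protocol wording change and a short listing, with no new data collection. The downside is a possible slight rise in DLT counts.

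In the same edit, it would help to state whether ALT/AST Grade ≥3 in Section 4.3.2 is read against ULN or against baseline. No change to those limits is proposed here.
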